1.5.2 Commercial Reports

Data on the commercial and compatible use of NovaSure EA with Essure micro-inserts in place have been reported. D. Saunders conducted a retrospective case review study of 118 sequential patients who had Essure micro-insert placement followed by NovaSure endometrial ablation. The interval between the Essure placement and NovaSure procedures ranged from 2 to 108 days. All patients were informed of the Essure Instructions for Use requirements for the Essure Confirmation Test to be performed 90-days after micro-insert placement; most patients chose not to wait because of their desire for the NovaSure endometrial ablation to eliminate their excessive uterine bleeding sooner. Two patients required replacement of the micro-insert at the time of the NovaSure procedure because the micro-insert was attached to the NovaSure instrument when it was withdrawn. A second

device was placed without difficulty. At up to two years of follow up (for the earliest study participant), none of the study subjects have had a pregnancy. No complications occurred and no adverse events have required treatment or hospitalization [[4]].

Basinski, et al, conducted a retrospective review of 117 patients who had undergone Essure micro-insert placement followed by NovaSure in two in-office sessions separated by a median time of 14 days. In this study, 83/117 (71%) returned for the Essure Confirmation Test. Satisfactory placement and tubal occlusion was demonstrated in 79/83 (95%) of these patients. Amenorrhea or spotting was observed in 72/97 (74%) of patients, 22/97 (23%) reported satisfactory decrease in menstrual flow, and 3/97 (3%) patients reported failure of the ablation procedure. A total of eight adverse events was obtained on 111/117 (95%) patients that had follow up. None of the adverse events reported in the study appeared to be related to the performance of NovaSure after Essure specifically. There have been no reported pregnancies for the patients that have been relying on Essure for permanent contraception from 6 to 24 months. The study results showed that the combination of Essure followed by NovaSure did not decrease effectiveness of either procedure and no serious adverse events were attributed to the combination of the two procedures in this study [[5]].

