7.4.1.1.4 Device deficiency - amended

Inadequacy of Essure or Novasure related to its identity, quality, durability, reliability, safety or performance, such as malfunction, misuse or use error and inadequate labeling.³³

7.4.1.1.4.1 Device failure - amended

Failure of Essure or Novasure to perform or function as intended, including any deviations from the performance specifications or intended use (e.g., pregnancy when micro-insert properly located and fallopian tubes occluded; continued menorrhagia despite a completed endometrial ablation procedure). For the purposes of this study, a pregnancy that occurs in a subject told to rely on a commercially available Essure device for contraception is a device

³⁶ Modified per Amendment 6, see Section 7.4.1.1.2 UADE.

failure. For the purposes of this protocol, persistence or recurrence of heavy menstrual bleeding will be considered device failures for the Novasure device.³³

7.4.1.1.4.2 Device malfunction - amended

Failure of Essure or Novasure to meet its performance specifications or otherwise perform as intended when used in accordance with the IFU (e.g., difficulties with deployment or detachment of micro-insert; device difficulties when conducting endometrial ablation).³³

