6.3.1 Adverse Events

All AEs will be coded using MedDRA.

Frequency tables showing an overall summary of the number of events (where possible) and the number of subjects with AEs by system organ class (SOC) and preferred term (PT) will be given for the following types of AEs:

- All AEs
- AEs (possibly, probably, definitely) related to:
 - Essure device
 - NovaSure device
 - NovaSure procedure
 - Pre-existing condition
- AEs by intensity (mild, moderate, severe)
- AEs by outcome

- AEs of special interest
 - Defined as follows (updated annually by Medical Experts):

AE of Special Interest	Description	AEDECOD (PT)	AELLT
Abnormal Uterine Bleeding	Set to Y if AEDECOD equal to any of values in Column C:	Dysfunctional uterine bleeding	
		Genital hemorrhage	
		Genital haemorrhage	
		Menometrorrhagia	
		Menorrhagia	
		Metrorrhagia	
		Polymenorrhoea	
		Uterine hemorrhage	
		Uterine haemorrhage	
		Vaginal hemorrhage	
		Vaginal haemorrhage	
		Amenorrhea	
		Amenorrhoea	
		Hypomenorrhea	
		Hypomenorrhoea	
		Oligomenorrhea	
		Oligomenorrhoea	
		Bleeding anovulatory	
		Menstrual disorder	
Menstruation delayed			
Menstruation irregular			
Lower Abdominal Pelvic and Back Pain	Set to Y if AEDECOD='Back pain' and AELLT='Low back pain', otherwise set to Y if AEDECOD equal to any of values below:	Back pain	Low back pain
		Abdominal pain	
		Abdominal pain lower	
		Abdominal tenderness	
		Abdominal discomfort	
		Incision site pain	
		Implant site pain	
		Medical device discomfort	
		Medical device pain	
		Medical device site discomfort	
		Medical device site pain	
		Suprapubic pain	
		Visceral pain	
		Post ablation tubal ligation syndrome	
		Pubic pain	

		Groin pain	
		Genito-pelvic pain/penetration disorder	
		Uterine cervical pain	
		Ovulation pain	
		Pelvic pain	
		Pelvic discomfort	
		Dyspareunia	
		Adnexa uteri pain	
		Uterine tenderness	
		Uterine pain	
		Uterine spasm	
		Dysmenorrhoea	
		Menstrual discomfort	
		Premenstrual cramps	
Perforation	Set to Y if AEDECOD equal to any of values in Column C:	Fallopian tube perforation	
		Uterine perforation	
Upper genital tract infections	Set to Y if AEDECOD equal to any of values in Column C:	Endometritis	
		Salpingitis	
		Salpingo-oophritis	
		Pelvic inflammatory disease	
Expulsion or migration or unintentional removal of Essure inserts	Set to Y if AEDECOD equal to any of values in Column C:	Device dislocation	
		Device expulsion	
		Unintentional medical device removal	

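### The SAP's abnormal-bleeding special-interest flag pools absent or reduced bleeding with heavy bleeding, so its subject count has no direction

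*SAP*

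**What the plan says.** SAP 6.3.1 lists the adverse events of special interest with the coded terms that define each. The category "Abnormal Uterine Bleeding" has one rule: "Set to Y if AEDECOD equal to any of values in Column C". The list includes Menorrhagia, Menometrorrhagia, Polymenorrhoea and the genital, uterine and vaginal haemorrhage terms. It also includes Amenorrhoea, "Hypomenorrhoea", "Oligomenorrhoea" and Menstruation delayed. Nothing in the table separates one direction of bleeding from the other. The same section provides for annual revision of the list by medical experts, and has each type of adverse event summarised by system organ class and preferred term.

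Protocol 5.1.1 requires menorrhagia from benign causes and willingness to have NovaSure for it. Protocol 7.4.1.1.4.1 gives "continued menorrhagia despite a completed endometrial ablation procedure" as an example of device failure and adds that "persistence or recurrence of heavy menstrual bleeding will be considered device failures for the Novasure device". In the background, Protocol 1.5.2 summarises a retrospective review of Essure followed by NovaSure: "Amenorrhea or spotting was observed in 72/97 (74%) of patients, 22/97 (23%) reported satisfactory decrease in menstrual flow", and 3/97 (3%) reported failure of the ablation.

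**The concern.** A special-interest flag exists to give one number: how many women had at least one event of that kind. In most populations, a broad menstrual-disturbance category is harmless. Here the women enter because they bleed too much and receive a procedure meant to reduce bleeding, so a heavy-bleeding term and an absent-bleeding term point in opposite directions. The heavy end is also a protocol-defined device failure.

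Adverse-event incidence is the only secondary endpoint (Protocol 8.4.2, SAP 6.2.2), and special-interest events are a named safety variable (SAP 6.3). A high count could reflect many women with returning haemorrhage, or many whose absent or light periods were written down as events. The count alone cannot tell these apart.

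**Working it through.** **Step 1. The plan's own figures.** Protocol 1.5.2 gives 72/97 = 74.2%, 22/97 = 22.7% and 3/97 = 3.1%, matching its stated 74%, 23% and 3%. The groups are exhaustive: 72 + 22 + 3 = 97.

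**Step 2. The list by direction.** The table has 21 entries, which reduce to 15 distinct terms once US and UK spellings are merged.

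| Direction | Terms | Number |
|---|---|---|
| Excess, too frequent, intermenstrual or otherwise abnormal | Dysfunctional uterine bleeding; Genital, Uterine and Vaginal haemorrhage; Menometrorrhagia; Menorrhagia; Metrorrhagia; Polymenorrhoea | 8 |
| Absent, reduced, infrequent or delayed | Amenorrhoea; Hypomenorrhoea; Oligomenorrhoea; Menstruation delayed | 4 |
| No direction | Bleeding anovulatory; Menstrual disorder; Menstruation irregular | 3 |

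**Step 3. Can the count be rebuilt from preferred-term rows?** Not exactly. A woman with both Menorrhagia and Metrorrhagia appears in two rows. The number of women with any heavy-bleeding event lies somewhere between the largest single row and the sum of the rows. Only a subject-level flag fixes it.

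**Step 4. How much could the pooling matter?** The documents do not say how often absent or light periods are recorded as adverse events. Call that share *f* and treat it as an assumption. Take the enrolment minimum of 220 and the review's proportions, and suppose that every ablation failure is recorded as a heavy-bleeding event and that the groups do not overlap.

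- Heavy side: 220 × 3/97 = 6.8 women.
- Reduced side, amenorrhea or spotting only: 220 × 72/97 × *f* = 163.3 × *f*.
- Reduced side, adding the satisfactory-decrease group: 220 × 94/97 × *f* = 213.2 × *f*.

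| *f* | Reduced side (72/97) | Flag total | Reduced share | Reduced share using 94/97 |
|---|---|---|---|---|
| 0% | 0 | 6.8 | 0% | 0% |
| 1% | 1.6 | 8.4 | 19% | 24% |
| 5% | 8.2 | 15.0 | 55% | 61% |
| 10% | 16.3 | 23.1 | 71% | 76% |
| 100% | 163.3 | 170.1 | 96% | 97% |

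The two sides are equal when 72*f* = 3, that is *f* = 4.2%. A heavy-bleeding sub-row stays at 6.8 whatever *f* is.

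**Step 5. A check on plausible *f*.** The same review reports eight adverse events in 111 women with follow-up. Had all eight been amenorrhoea in different women, that would be 8/111 = 7.2% of women, or 7.2/74.2 = 9.7% of those with amenorrhea or spotting. At *f* = 5%, 5% × 74.2% = 3.7% of women would be recorded, which is inside that limit. At *f* = 10% it would be 7.4%, just outside. The review was retrospective, so this is not a firm ceiling for a prospective study, but it gives no support for high values of *f*.

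**The case against.** The strongest reply is that little is lost. SAP 6.3.1 tabulates special-interest events by preferred term, so Amenorrhoea and Menorrhagia sit on separate lines. NovaSure failure has its own route: Protocol 7.4.1.3 requires device failures on a dedicated form, SAP 6.3 plans summaries of NovaSure device events, and SAP 6.3.1.1 tabulates adverse device events by category, including device failure. The flag is not the planned measure of ablation failure. Protocol 7.4.1.1.1 also limits adverse events to untoward occurrences, so a wanted end to bleeding should not ordinarily be recorded, and one that is recorded was presumably judged untoward. The output is descriptive, with no hypothesis, and the category is not among the protocol's own special-interest events (Protocol 7.4.1.1.5).

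Most of this stands, and it limits the point to the category count. It does not restore that count: preferred-term rows cannot be added up to women, and the SAP lists the absent and reduced terms, so it provides for their being reported.

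A reader might also infer three stronger claims, which the documents do not support:

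- *That the protocol classes all these terms as NovaSure success.* It has no such definition. The support is one background review. It fits amenorrhoea, although its 74% includes spotting. It fits hypomenorrhoea loosely, through the satisfactory-decrease group. It does not mention oligomenorrhoea, and ablation success is not a study endpoint.
- *That most flagged women will have had a wanted outcome.* That needs *f* above about 4%, which nothing in the documents establishes.
- *That the count spoils comparisons between sites.* No such comparison of adverse events is planned; SAP 6.1 uses site only for enrolment.

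**Conclusion.** The point holds at the level of the category count. The flag merges opposite directions of bleeding in a population where direction decides the meaning, and one direction is a protocol-defined device failure. The number of flagged women cannot be read as more or less bleeding, and the number with heavy bleeding cannot be recovered exactly from the preferred-term rows.

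The size is unknown. The illustration runs from no effect at *f* = 0 to a total made up mostly of absent or reduced bleeding once *f* passes about 4%. It rests on an assumed recording share, on one retrospective series, and on failures being recorded as heavy-bleeding events. No tested result changes. This is a worthwhile, low-cost improvement to a descriptive safety table, not a threat to the study's conclusions.

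**What to change.** In SAP 6.3.1, keep the overall flag if it is wanted, and report the number of women in three declared sub-rows beneath it:

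1. Heavy, prolonged, too frequent or intermenstrual bleeding: Genital, Uterine and Vaginal haemorrhage, Menorrhagia, Metrorrhagia, Menometrorrhagia, Polymenorrhoea, Dysfunctional uterine bleeding.
2. Absent, reduced, infrequent or delayed menses: Amenorrhoea, Hypomenorrhoea, Oligomenorrhoea, Menstruation delayed. Do not label this row as expected; Protocol 7.4.1.5 leaves expectedness to the sponsor, judged against the instructions for use.
3. Unspecified direction: Bleeding anovulatory, Menstrual disorder, Menstruation irregular.

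State that a woman can appear in more than one sub-row, so the rows need not sum to the total. A footnote should say that the protocol gave no rule on recording absent or light periods as adverse events, because the split does not remove that uncertainty from row 2. Fix the assignment before data release, in line with Protocol 8.1, so that the grouping is not chosen after the counts are seen.

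The cost is three derived flags and a few extra rows in one descriptive table. No new data are needed, no event is dropped, and the primary endpoint is untouched.

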7.4.1.1.5 Important Medical Events and events of special interest - amended

The Important Medical Events (IME) list is developed and published by European Medicines Evaluation Agency (EMA) (<http://eudravigilance.ema.europa.eu/human/textforIME.asp>). All AEs reported in this study will be reviewed against the most current IME list periodically, and any events that are contained on the IME list will be specifically reviewed and the Investigator will be asked to review and confirm whether or not the event meets the criteria for seriousness in his/her opinion. In addition, the following events of special interest will be closely reviewed by the sponsor's study medical expert:

- Perforations of the uterus, cervix or fallopian tubes.³⁷
- Upper genital tract infections (for example: endometritis, salpingo-oophoritis, salpingitis).
- Expulsion or migration of Essure inserts.
- Potential allergy/hypersensitivity to Essure inserts (for example: itch [pruritus], rash, hives [urticaria], facial edema, angioedema, allergy to metals).³⁷

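### The SAP's perforation flag has no cervical term, although the protocol's special-interest category names the cervix; the allergy and infection lists have smaller gaps

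*SAP*

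**What the plan says.** Protocol 7.4.1.1.5, in its current text, names four groups of special-interest events for close review by the sponsor's medical expert. One is "Perforations of the uterus, cervix or fallopian tubes". Two others, upper genital tract infection and potential allergy to the inserts, are illustrated by examples. The infection examples are endometritis, salpingo-oophoritis and salpingitis. The allergy examples are pruritus, rash, urticaria, facial edema, angioedema and allergy to metals. The fourth group, expulsion or migration of inserts, is not at issue here.

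SAP section 1 states that the plan is based on Amendment 6, which added the perforation and allergy groups. SAP 6.3 names special-interest adverse events as a safety variable, and SAP 6.3.1 gives them their own table. The perforation, infection and allergy flags follow one rule: "Set to Y if AEDECOD equal to any of values in Column C". The perforation row lists "Fallopian tube perforation" and "Uterine perforation" and nothing else. The introduction to the list reads "Defined as follows (updated annually by Medical Experts".

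**The concern.** The three perforation sites are the protocol's definition of the category, not illustrations of it. A rule that requires equality with a listed preferred term captures only what is listed, and no listed perforation term names the cervix. A reader of the perforation row would take it to cover the protocol's category, and from the SAP as written that cannot be confirmed.

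The same rule makes two smaller points relevant. Facial edema and angioedema are named in the protocol but have no term in the SAP's allergy list. The infection list shows "Salpingo-oophritis", which differs by one letter from the protocol's spelling; under exact matching, a misspelled entry would not match a correctly spelled term.

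At stake is the completeness of one safety table. The serious-AE repeat of the tables leaves out the special-interest breakdown, so no second table built on these lists would show an omission.

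**Working it through.** There is no stated figure to reproduce. The check sets current protocol text against current SAP text, item by item. Definitions are kept apart from examples.

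**Perforation (definition, three sites)**

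| Protocol 7.4.1.1.5 | SAP 6.3.1 term |
|---|---|
| Uterus | "Uterine perforation" |
| Fallopian tubes | "Fallopian tube perforation" |
| Cervix | none |

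Unmatched: 3 − 2 = 1 of 3.

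Could the uterine term be meant to include the cervix? The SAP does not say so. In its pain list the same table gives "Uterine cervical pain" as well as a separate uterine pain term, so there it treats the two sites as distinct. That shows how the table was built for pain. It does not show how a cervical perforation would be coded.

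**Infection (three examples)**

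The SAP lists four terms: endometritis, salpingitis, "Salpingo-oophritis" and pelvic inflammatory disease. Endometritis and salpingitis match. Salpingo-oophoritis is plainly intended. Unmatched: 0 of 3 if the spelling is only an artefact of the machine-read text, or 1 of 3 if it is in the source file.

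**Allergy (six examples)**

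The SAP lists ten terms: allergy to animals, to chemicals and to metals; hypersensitivity; multiple allergies; pruritus; rash; pruritic rash; seasonal allergy; and urticaria. Pruritus, rash, urticaria and allergy to metals match. Facial edema and angioedema do not. Unmatched: 6 − 4 = 2 of 6.

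**Examples together**

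3 + 6 = 9 items. Unmatched: 0 + 2 = 2 of 9, or 1 + 2 = 3 of 9 if the misspelling is confirmed.

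**Spelling variants elsewhere in the table**

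Six bleeding terms appear in two spellings each: genital, uterine and vaginal hemorrhage (for example "Genital haemorrhage" beside its American form), amenorrhea, hypomenorrhea and oligomenorrhea. So exact spelling was taken into account for some terms. The practice is not uniform: polymenorrhoea and dysmenorrhoea appear once each.

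**Where an unflagged event would still be seen**

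It would appear by system organ class and preferred term in the all-AE table, and in the related and serious tables where it qualifies. If related to a device or procedure, it would also appear in the adverse-device-event tables of SAP 6.3.1.1. Those tables have their own special-interest category, and the SAP does not say whether that category uses these lists.

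**The case against.** The strongest reply is that a gap in wording is a gap in analysis only if cervical perforation codes to something other than the listed uterine term. Neither document gives the MedDRA mapping, and the pain-list comparison cannot supply it. This stands as a limit on the consequence: the undercount may be zero. It does not remove the mismatch, because the SAP neither lists a cervical term nor says which term covers the cervix.

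Second, the list is subject to annual expert revision, so the printed table may be a snapshot and the operative list is not in the documents. That is fair. But the clause permits a correction without showing one, and it does not tie the revision to protocol 7.4.1.1.5. The SAP's document history dates Version 1.1 to 15 December 2020, more than four years after the Amendment 6 date it cites (12 July 2016) and one month before the projected final follow-up in January 2021 (protocol section 15).

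Third, the protocol section prescribes medical review, not a tabulation, and that review covers cervical perforation whatever the flag does. The SAP table is also not a copy of the protocol list; it adds bleeding, pain and auto-immune categories. Both points are correct and limit the harm. They do not explain why a category carried over from the protocol should be narrower than its source.

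Fourth, the allergy and infection items are only examples, and the spelling may be an artefact. They are rightly secondary, and the counts out of nine should not be read as a measure of bias. An item the protocol names as an example is nevertheless a member of its category.

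**Conclusion.** The concern holds, as a minor point. SAP 6.3.1 states a matching rule and lists that are narrower than the protocol categories they implement. The firm gap is one of three defining perforation sites. The secondary gaps are two of nine examples, or three of nine if the misspelling is in the source file.

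Confidence is high in the textual mismatch. The effect on counts cannot be sized, because the documents give neither event rates nor the MedDRA coding; it ranges from zero upward. The conclusion assumes that the printed lists are the ones applied and that matching is by equality, as the SAP states. The effect is confined to the special-interest table. No event is lost from the all-AE table, the sponsor's medical review does not depend on the flag, and the primary endpoint is unaffected.

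**What to change.** Before the final analysis:

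- Add the preferred term or terms to which cervical perforation codes in the MedDRA version used, or state which listed term captures it.
- Add the terms for angioedema and for facial edema.
- Check "Salpingo-oophritis" against the source file and the analysis code list, and correct it if the error is there.
- Reconcile the final list with protocol 7.4.1.1.5 and record the date of the last expert update.

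The cost is an edit to one SAP table and the matching code list. No new data are needed.

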7.4.1.3 Assessments and documentation of adverse events³⁸ - amended

Investigators must collect all AEs for each subject from the time of signing of the informed consent through the end of subject study participation, whether or not deemed related to the investigational device or procedure. All AE data will be recorded on the CRFs as well as documented in the subject's medical record and study source documents.³⁹

All SAEs and SADEs will be followed until the event has subsided or, in case of permanent impairment, until the event stabilizes and the overall clinical outcome has been ascertained.

Investigator must determine whether adverse event meets the definition of a serious adverse event; if so, it must be reported as required by Section 7.4.1.1.

Any SAE or incident will be reviewed and processed by the sponsor according to all applicable regulations.

Investigators must document all device failures, malfunctions and use errors, including the assessment of whether the event is considered an incident (ADE) using the Device Malfunction and Failure CRF.

Because an approved device will be used for the placement procedure, any device malfunctions will be reported to the sponsor's Product Surveillance department. Device malfunctions will not be analyzed as part of this study as the placement procedure and devices are not being evaluated.

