Potential allergy/hypersensitivity to Essure inserts	Set to Y if AEDECOD equal to any of values in Column C:	Allergy to animals	
		Allergy to chemicals	
		Allergy to metals	
		Hypersensitivity	
		Multiple allergies	
		Pruritus	
		Rash	
		Rash pruritic	
		Seasonal allergy	
		Urticaria	
Auto-immune	Set to Y if AEDECOD equal to any of values in Column C:	Autoimmune disorder	
		Autoimmune thyroiditis	
		Multiple sclerosis	
		Multiple sclerosis relapse	
		Rheumatoid arthritis	

- AEs occurring in at least 1% of subjects

The same AE tables listed above will be repeated for treatment-emergent serious AEs, except for AEs of special interest.

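### The SAP's insert-allergy flag counts seasonal and animal allergy but omits facial edema and angioedema, so its total does not match the protocol's event of special interest

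*SAP*

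**What the plan says.** Protocol 7.4.1.1.5 lists the events of special interest that the sponsor's medical expert is to review closely. One entry, added by Amendment 6, reads "Potential allergy/hypersensitivity to Essure inserts (for example: itch [pruritus], rash, hives [urticaria], facial edema, angioedema, allergy to metals" and ends there. The amendment's stated reason (13.4.1.9) is to help find women who develop a potential reaction to the inserts.

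SAP 6.3.1 turns this into a programmable flag under the same category name. The rule is "Set to Y if AEDECOD equal to any of values in Column C", so the coded preferred term decides. Relatedness and onset date are not conditions. The ten listed terms include "Seasonal allergy" and "Allergy to animals". No term for facial edema or angioedema is listed. The SAP notes that the definitions are "updated annually by Medical Experts".

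Two other provisions set the context. Under protocol 7.4.1.3, AEs are collected "whether or not deemed related to the investigational device or procedure", so an unrelated allergy recorded as an AE can reach the flag. SAP 6.3.1 also plans tables of "AEs (possibly, probably, definitely) related to" each device, the NovaSure procedure and pre-existing conditions. Those tables are separate and do not restrict the special-interest flag.

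**The concern.** The category heading names the Essure inserts, so a reader will take its count as the number of women with a possible reaction to the device. A woman whose only event is hay fever or a pet allergy would be in that count, although the coded term already attributes the event to something else. A woman whose only event is angioedema would not be in it, although the protocol names that event.

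Adverse event data are the study's only secondary endpoint, and this category was added specifically to look for insert reactions. In a cohort of this size a few women either way change the reported percentage visibly.

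**Working it through.** The plan states no rate for this category, so there is no figure to reproduce. The check compares the two lists and then sizes the effect of one woman.

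**Step 1. The lists side by side** (SAP 6.3.1 against the examples in protocol 7.4.1.1.5)

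| Group | Terms | Count |
|---|---|---|
| In both | pruritus, rash, urticaria, metal allergy | 4 |
| SAP only, no trigger named or insert material not clearly excluded | hypersensitivity, pruritic rash, multiple allergies, chemical allergy | 4 |
| SAP only, another trigger named | seasonal allergy, animal allergy | 2 |
| Protocol only | facial edema, angioedema | 2 |

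The SAP list has 4 + 4 + 2 = 10 terms. The protocol gives 4 + 2 = 6 examples. The second row is a reasonable widening of an open list of examples. The third row is not, because those terms identify a different cause. The fourth row is a plain omission.

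**Step 2. Effect of one woman on the total**

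The SAP summarises safety on the Safety Cohort. Its size is not known in advance, so I take the planned minimum enrolment of 220 (protocol section 4, SAP section 3) as an approximate denominator.

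A woman flagged only by seasonal or animal allergy adds 1/N:

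- 1 woman: 1/220 = 0.45 percentage points (1/200 = 0.50 if the cohort is nearer the 200 used in the power calculation)
- 2 women: 2/220 = 0.91
- 5 women: 5/220 = 2.27
- 10 women: 10/220 = 4.55

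**Step 3. How likely is at least one such woman?**

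The documents give no rate p. As an assumption only, take p, the share of women with such an AE and no other listed term, between 0.5% and 5%. The expected number is 220p, and P(at least one) = 1 − (1 − p)^220.

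| Assumed p | Expected women | P(at least one) |
|---|---|---|
| 0.5% | 1.1 | 0.67 |
| 1% | 2.2 | 0.89 |
| 2% | 4.4 | 0.99 |
| 5% | 11.0 | > 0.99 |

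The expected numbers only restate the assumption. The table shows that even a low rate would probably put at least one such woman in the category.

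**Step 4. Net error**

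Let a be the number of women flagged only by the two terms, and b the number with facial edema or angioedema and no listed term. The error in the category percentage is 100 × (a − b)/220. With a = 5 and b = 0 it is +2.27. With a = 0 and b = 2 it is −0.91. With a = b it is zero, although the wrong women are counted. Neither a nor b can be obtained from the documents.

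**The case against.** The best defence is that this is a deliberately broad screen. The category concerns potential allergy, the protocol's list is introduced as examples, the purpose is detection, and medical experts revisit the list yearly. Causality is handled elsewhere: investigators rate each AE's relation to the Essure device (protocol 7.4.1.2.3), and the SAP tabulates device-related AEs and adverse device effects separately. Allergies that began before consent are medical history (protocol 7.2.2), so long-standing hay fever would not ordinarily enter as a new AE.

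Much of this stands. It justifies unspecific terms such as rash, pruritus and hypersensitivity, and it means the number of women affected may be small. It does not justify terms whose wording already names another trigger, and a screen meant to be broad should not omit two of the protocol's own examples.

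Three stronger readings are tempting, and the documents do not support them.

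- **That the rate is inflated.** The omissions pull the other way, so the sign of the net error is unknown.
- **That a metal-allergy signal would be hidden.** SAP 6.3.1 specifies the special-interest tables by system organ class and preferred term, so metal, seasonal and animal allergy would appear on separate lines. Only the category total can mislead.
- **That the back-pain rule cancels its own low-back restriction.** The rule reads "Set to Y if AEDECOD='Back pain' and AELLT='Low back pain', otherwise set to Y if AEDECOD equal to any of values below". A reader might infer that, because back pain is itself a listed term, the second branch flags all back pain. This row, however, points to the values beneath it, where the other category rows point to Column C. Back pain stands beside the rule with its lower-level-term cell filled, and the unrestricted terms follow underneath. The natural reading keeps the restriction. It fails only if the second branch covers the whole column, and text extracted from PDF cannot settle the cell layout. The rule is not shown to be wrong.

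**Conclusion.** The point holds for the allergy category. As written, the flag counts two terms that name a trigger other than the insert and misses two events that the protocol names, so the category total does not measure the protocol's event of special interest.

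The size is about 0.45 percentage points per woman misclassified in either direction, taking 220 as the denominator. The number of such women is not in the documents. The conclusion also assumes that the report will show a count for the flagged category as well as its preferred-term lines. The SAP shows no table layout, but a category flag has little other use.

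The consequence is confined to reading a descriptive safety table. SAP 6.2.2 states no hypothesis for adverse events, and neither the pregnancy endpoint nor its success rule is touched.

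**What to change.** In the special-interest table of SAP 6.3.1:

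1. Move seasonal allergy and animal allergy to a separate row, labelled for instance as allergy with another named trigger, and exclude that row from the insert-allergy total.
2. Add the preferred terms that the MedDRA version in use assigns to facial edema and angioedema, so that the list covers every example in protocol 7.4.1.1.5.
3. Optionally, reword the pain rule so that it has one reading: (PT = Back pain AND LLT = Low back pain) OR any other listed PT. This is for clarity only.

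The cost is an edit to the definition table and the matching lines of code, for which the yearly expert update already offers a route. The drawback is a slightly narrower screen: a reaction to the insert that was miscoded as seasonal or animal allergy would leave the category total. It would still appear in the separate row and in the tables by system organ class and preferred term, and no data are lost.
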